11 STATISTICS

This section outlines the statistical analysis methodology for this study. Further details of the statistical analyses will be described in the SAP that will be finalized prior to the database lock and unblinding. Statistical analysis will be performed using SAS® software version 9.4 or above and other validated statistical software as needed. All clinical data will be summarized using descriptive statistics (n, mean, standard deviation [SD], median, minimum, and maximum for continuous measurements, and counts and percentages for categorical measurements).

11.1 Analysis Population

- Full Analysis Set (FAS): The FAS will include all randomized subjects.
- **Per-protocol Analysis Set (PPS):** The PPS will include the subset of subjects from the FAS who do not meet the criteria that would confound the evaluation of the efficacy endpoints. A full list of the criteria will be finalized prior to database lock and unblinding.
- Safety Analysis Set: The Safety Analysis Set will include all subjects who receive at least 1 dose of study drug.

11.2 Statistical Methods

This study consists of a double-blind, placebo-controlled period (Core Phase) and an open-label extension period (Extension Phase). The database will be locked, and the treatment assignment will be unblinded, when the last subject completes the Core Phase of the study. All data from the Core Phase and Extension Phase available in the locked database will be included in the statistical analyses. When the last subject completes the Extension Phase, additional extension data will be summarized and included in the Clinical Study Report addendum.

11.2.1 Disposition, Demographics, and Baseline Characteristics

Subject disposition will be summarized overall and by treatment group. In addition, the number of subjects screened, the number of subjects who failed screening, and the reasons for screen failure will be summarized. Demographic and Baseline characteristics will be summarized overall and by treatment group. Medical history and prior and concomitant medications will be coded using Medical Dictionary for Regulatory Activities (MedDRA) and WHODrug dictionaries and summarized overall and by treatment group.

11.2.2 Efficacy Analysis

All efficacy analyses will be conducted using the FAS, unless otherwise specified.

In order to satisfy the primary endpoint requirements of different regulatory agencies, 2 primary efficacy endpoints will be evaluated. Two separate SAPs will be developed to describe the statistical methodology for the analysis of each primary efficacy endpoint. In the first SAP, the endpoint described as "Primary Efficacy Endpoint" in Section 3.1 will be assessed as the primary efficacy endpoint, and the endpoint described as the "Alternative Primary Efficacy Endpoint" in Section 3.2 will be assessed as the first secondary efficacy endpoint. In the second SAP, the endpoint described as "Alternative Primary Efficacy Endpoint" in Section 3.2 will be assessed as the primary efficacy endpoint, and the endpoint described as the "Primary Efficacy Endpoint" in Section 3.1 will be

assessed as the first secondary efficacy endpoint. Both SAPs will evaluate the additional secondary efficacy endpoints described in Section 3.3.

For the efficacy evaluation of the platelet count responses, platelet counts assessed by local labs will be used. Platelet counts collected via the central lab will be used in the safety assessments of clinical laboratory tests.

Primary Efficacy Endpoint:

The primary efficacy endpoint is the durable platelet response as defined by the proportion of subjects achieving at least 6 out of 8 weekly platelet counts $\geq 50 \times 10^9 / L$ during the last 8 weeks of the 12 week Treatment Period in the Core Phase, in the absence of rescue medication. The null hypothesis is that the treatment effect of avatrombopag is the same as that of placebo. The alternative hypothesis is that the treatment effect of avatrombopag is different than that of placebo.

The primary efficacy endpoint will be tested between avatrombopag and placebo using the Cochran-Mantel-Haenszel 2-sided test at α =0.05, adjusting for age cohort and Baseline platelet count (\leq 15×10⁹/L vs >15×10⁹/L), or the Fisher's exact test, when data is sparse. In addition, the numbers and percentages of responders in each treatment group, the associated 95% confidence intervals (CI), and the 95% CI for the difference between avatrombopag and placebo will be summarized. The primary analysis will be performed based on the FAS and repeated on the PPS as a supportive analysis. Other sensitivity analyses of the primary efficacy endpoint may be performed as appropriate.

Subjects without sufficient data for the determination of response status (i.e., responder versus non-responder) will be treated as non-responders in the analysis. Every effort should be made during the conduct of the study to limit the extent of missing data. Subjects who prematurely discontinue the study drug should remain in the study for collection of data, unless the subject withdraws consent.

Alternative Primary Efficacy Endpoint:

The alternative primary efficacy endpoint is platelet response as defined by the proportion of subjects for whom at least 2 consecutive platelet assessments are $\geq 50 \times 10^9/L$ over the 12-week Treatment Period in the Core Phase in the absence of rescue medication. The null hypothesis is that the treatment effect of avatrombopag is the same as that of placebo. The alternative hypothesis is that the treatment effect of avatrombopag is different than that of placebo.

The alternative primary efficacy endpoint will be tested between avatrombopag and placebo using the Cochran-Mantel-Haenszel 2-sided test at α =0.05, adjusting for age cohort and Baseline platelet count (\leq 15× 10⁹/L vs >15×10⁹/L), or the Fisher's exact test, when data is sparse. In addition, the numbers and percentages of responders in each treatment group, the associated 95% CI, and the 95% CI for the difference between avatrombopag and placebo will be summarized. The primary analysis will be performed based on the FAS and repeated on the PPS as a supportive analysis. Other sensitivity analyses of the alternative primary efficacy endpoint may be performed as appropriate.

11.2.2.1 Secondary Efficacy Analysis

The secondary efficacy endpoints for this study are:

- The percentage of weeks subjects have a platelet count $\geq 50 \times 10^9 / L$ during 12 weeks of treatment in the Core Phase, in the absence of rescue therapy.
- Platelet response at Day 8 (defined by the proportion of subjects with a platelet count $\geq 50 \times 10^9 / L$ at Day 8, in the absence of rescue therapy).
- The percentage of weeks subjects have a platelet count between $\geq 50 \times 10^9 / L$ and $\leq 150 \times 10^9 / L$, during 12 weeks of treatment in the Core Phase, in the absence of rescue therapy.
- The proportion of subjects who require rescue medications during 12 weeks of treatment in the Core Phase of the study.
- Incidence and severity of bleeding symptoms associated with ITP measured using the WHO Bleeding Scale.

The categorical variables (e.g., proportion) will be summarized and analyzed in the same manner as the primary efficacy endpoint. The continuous variables (e.g., percentage of weeks subjects have a platelet count $\geq 50 \times 10^9 / L$) will be analyzed using nonparametric Wilcoxon Rank Sum tests.

If the test of the treatment effect on the primary efficacy endpoint is statistically significant, the statistical tests on the secondary efficacy endpoints will be considered inferential; otherwise, the tests will be considered descriptive and no statistical inference can be drawn with regard to the secondary efficacy endpoints.

To control the family-wise Type I error rate at a significance level of α = 0.05 (2-sided), a step-down closed testing procedure will be used when testing the secondary efficacy endpoints. Starting with the first secondary efficacy endpoint, if the test is significant at α = 0.05, then the test on the next endpoint will be considered inferential; otherwise, the tests on the subsequent endpoints will be considered descriptive only. This process will be repeated from the top of the hierarchy for the remaining endpoints. The hierarchy of the closed testing will be defined in the SAPs.

The efficacy variables collected during the Extension Phase will be summarized descriptively. Additional efficacy analyses will be performed if deemed necessary. The details of the analyses will be described in the SAP that will be finalized prior to database lock.

11.2.3 Safety Analysis

Safety assessments for this study include the incidence of AEs, SAEs, AESI, clinical laboratory tests, and vital signs. The safety assessments will be summarized descriptively by treatment group for the Safety Analysis Set.

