Enrollment will not stop in the current cohort for the data review after Week 10, or for the data review after each cohort is fully enrolled.

Subjects who are not showing a platelet response (i.e., a lack of treatment effect) at the highest dose of study drug based on the subject's age cohort may be terminated from the Core Phase and directly enrolled into the open-label Extension Phase (Section 5.3).

Lack of treatment effect will be defined as:

- Platelet count remains <30×10⁹/L after more than 3 weeks at the maximum dose of study drug per Table 4. Subjects may also be terminated from the Core Phase and directly enrolled into the Extension Phase after 7 days of therapy at the maximum dose if they have dangerously low platelet counts (in the opinion of the Investigator), or
- Subjects who require rescue therapy more than 3 times or continuous rescue therapy for more than 3 weeks (Section 8.6).

[figure not shown]

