4.1.1 Core Phase

The Core Phase of AVA-PED-301 is designed to assess the efficacy, safety, and tolerability of avatrombopag in pediatric subjects with ITP.

In order to participate in the Core Phase of the study, informed consent/assent must be completed by the subject and/or the subject's Legally Authorized Representative (LAR).

Subjects who participate in the Core Phase will enter a Screening Period followed by a 12 week Treatment Period after which they may either complete the study with an End of Study Visit that will occur 30 days after the last dose of study drug or continue into the open-label Extension Phase. The Core Phase of the study will last 12 weeks (approximately 84 days), which does not include the 4 week Follow-up Period, with study visits occurring once weekly through the end of Week 12 (Figure 3).

Figure 3 AVA-PED-301: Core Phase Study Schematic

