5.3 Stopping Criteria

Subjects may be removed from the Core Phase and directly enrolled into the open-label Extension Phase due to a lack of treatment effect.

A lack of treatment effect will be defined as:

- Platelet count remains <30×10⁹/L after more than 3 weeks at the maximum dose of study drug per Table 4. Subjects may also be terminated from the Core Phase and directly enrolled into the Extension Phase after 7 days of therapy at the maximum dose if they have dangerously low platelet counts (in the opinion of the Investigator), or
- Subjects who require rescue therapy more than 3 times or continuous rescue therapy for more than 3 weeks (Section 8.6).

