7.1 General Statistical Procedures

Categorical variables will be summarized with number and percentage of subjects with a response in the category. Percentages will be based on number of subjects in the given population as noted. Number of subjects with missing information will also be included. Percentages will be reported to one decimal place.

A 2-sided 95% exact binomial (Clopper-Pearson) confidence interval (CI) for categorical variables without multiplicity adjustment will be provided where appropriate for efficacy analysis.

Continuous variables will be summarized with number of subjects (n), mean, standard deviation (SD), median, minimum (min) and maximum (max). Mean and median will be reported to 1 more decimal place than the raw data, while the SD will be reported to 2 more decimal places than the raw data. Minimum and maximum will be reported with the same number of decimals as the original data.

Unless otherwise stated, statistical summaries will be performed for each study phase (Core Phase and Extension Phase). Core Phase analysis will be performed by treatment for each cohort and overall. Open Label Extension Phase analysis will be performed by cohort and overall.

Data that is not summarized will be listed only. Unless otherwise specified in the text, all listings will be provided for the Full Analysis Set and will be ordered by subject number, study phase (Core Phase and Extension Phase) and visit and repeated by cohort for available data.

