7.5.2 Adverse Events

Adverse events (AEs) will be coded using MedDRA version 23.0 or higher and will be classified by SOC and PT of MedDRA. The coding may be updated according to newly released versions of the dictionary. Severity of AEs will be graded according to Common Terminology Criteria for Adverse Events (CTCAE) v5.0.

A treatment emergent adverse event (TEAE) is defined as any AE that occurs after administration of the first dose of study drug.

AEs are classified as related or not related to the study drug based on investigator assessment. AEs with missing or unknown relationship to the study drug will be considered as related AEs.

TEAEs with starting date prior to the first dose date in the Open Label Extension Phase will be classified as TEAEs in the Core Phase. TEAEs with starting date on or after the first dose date in the Open Label Extension Phase will be classified as TEAEs in the Open Label Extension Phase. An overall summary of TEAEs will be provided for each phase and the entire study including:

• Any TEAE

- Any related TEAE
- Any Grade 3-5 TEAE
- Any TEAE leading to study discontinuation
- Any TEAE leading to drug withdrawn
- Any TEAE leading to dose reduction/interruption
- Any serious TEAE
- Any serious TEAE by relationship to study drug (related, unrelated)
- Any death
- Any AESI (AE of special interest) (Thromboembolic events, CTCAE Grade ≥3 Bleeding events)

The following events will be tabulated and summarized. The output will be sorted by decreasing frequency of PT within SOC which is sorted alphabetically in overall events.

- TEAEs by SOC and PT
- TEAEs by PT
- Drug-related TEAEs by SOC and PT
- Drug-related TEAEs by PT
- TEAEs by maximum toxicity grade, SOC and PT
- TEAEs leading to study discontinuation by SOC and PT
- Serious TEAEs by SOC and PT
- Drug-related serious TEAEs by SOC and PT
- AESIs by AESI category and PT

Two categories for Adverse Events of Special Interest (AESI) will be summarized and are defined based on terms in Standardized MedDRA Queries (SMQs) from MedDRA v26.1 or later:

- Thromboembolic events Any thrombotic or embolic event, whether arterial or venous SMQ = Embolic and thrombotic events
- Bleeding Events Any clinically significant blood loss [e.g., bleeding events with CTCAE grade 3+ (based on AE severity [AESEV]>=3] - SMQ = Haemorrhage terms (excl laboratory terms)

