If a SOC or PT is reported more than once for a subject, the subject will be counted only once in the incidence for that SOC or PT.

The following listing will be provided for the Safety Analysis Set:

- AEs
- Serious TEAEs

- Death
- Grade 3-5 TEAEs
- TEAE leading to study discontinuation
- AESIs

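### Core Phase adverse events are summarised only as crude percentages of subjects, although early exit to open-label drug is likely to shorten placebo observation more than avatrombopag observation

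*Protocol*

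**What the plan says.** Protocol 11.2.3 gives the safety plan in one line: "The safety assessments will be summarized descriptively by treatment group for the Safety Analysis Set". That sentence does not name the measure; the SAP does. On denominators, SAP 7.1 says "Percentages will be based on number of subjects in the given population as noted". On counting, SAP 7.5.2 says "If a SOC or PT is reported more than once for a subject, the subject will be counted only once in the incidence". The adverse event tables listed in SAP 7.5.2 include no exposure-adjusted rate, no time-to-event summary and no incidence to a common week.

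Protocol 5.3 provides the early exit: "Subjects may be removed from the Core Phase and directly enrolled into the open-label Extension Phase due to a lack of treatment effect". Protocol 6.3.2 exempts these children from the general expectation that subjects who stop study drug stay in for data collection. SAP 7.5.2 then sets the boundary: "TEAEs with starting date on or after the first dose date in the Open Label Extension Phase will be classified" as Extension Phase events. SAP 7.5.1 summarises treatment duration by phase, and SAP 7.1 makes Core Phase summaries by treatment, but nothing connects duration to adverse events.

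**The concern.** The Core Phase is the only randomised safety comparison in this study. Exit for lack of effect is driven by non-response, which is expected mainly on placebo. A child who leaves at Week 7 has five fewer weeks in which a Core Phase event can be counted, yet still adds one full subject to the denominator. If more placebo children leave, the placebo percentage falls with no difference in the underlying event rate.

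For most events this makes avatrombopag look worse than it is. For events that may be commoner on placebo, such as bleeding (an event of special interest), it hides a benefit. The SAP already allows for unequal treatment time in efficacy: the percentage-of-weeks endpoints in SAP 7.4 are divided by weeks on treatment. The safety tables have no counterpart.

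**Working it through.** **The plan's own figures.** The documents state no adverse event rate, exit share or expected exposure by arm, so there is no safety figure to reproduce. The sample-size statement (Protocol 11.3: 41.3% vs 3.4%, 54 vs 18, at least 90% power by Fisher's exact test) was checked and gives 94.5% at two-sided 0.05. It bears on this point only as the source of the response assumptions.

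**When exit can happen.** Protocol Tables 3 and 4 start children at Dose Level 4, allow one step up after two weeks, and have Level 6 as the top scheduled level. A non-responder reaches Level 5 at Week 2 and Level 6 at Week 4. Under Protocol 5.3, exit is then possible from about Week 5 (7 days at maximum dose with dangerously low counts) or after Week 7 (more than 3 weeks at maximum dose). The rescue criterion may act earlier. An exiting child loses about 12 − 7 = 5 to 12 − 5 = 7 weeks of Core observation.

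**Which arm loses more.** Protocol 11.3 assumes durable response of 41.3% vs 3.4% and cites a two-consecutive-week response of 88% vs none. Exit requires counts below 30 × 10⁹/L or repeated or prolonged rescue, not merely counts below 50, so these rates only bound the exit shares. They do point to more exits on placebo.

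**Model.** The assumptions are the same constant weekly hazard h in both arms, 12-week risk R, share f of an arm leaving, and exit at week t.

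- h = −ln(1 − R)/12
- Crude risk = (1 − f)·R + f·(1 − e^(−ht))
- False gap = (f_placebo − f_avatrombopag) × [R − (1 − e^(−ht))]

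With R = 0.50 and t = 7.5, h = 0.6931/12 = 0.0578 and 1 − e^(−7.5h) = 0.3516. The bracket is 0.50 − 0.3516 = 0.1484, or 14.8 points.

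| Placebo exits | Placebo crude % | Mean placebo weeks (12 − 4.5f) | Gap, 0% avatrombopag exits | Gap, 12% avatrombopag exits | Gap, 30% avatrombopag exits |
|---|---|---|---|---|---|
| 30% | 45.5 | 10.65 | 4.5 | 2.7 | 0 |
| 50% | 42.6 | 9.75 | 7.4 | 5.6 | 3.0 |
| 70% | 39.6 | 8.85 | 10.4 | 8.6 | 5.9 |

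All exit shares are assumptions. The 12% is 100 − 88, the cited two-week non-response on active drug.

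**Sensitivity.** At R = 50% the multiplier is 24.9 points for exit at Week 5, 16.7 at Week 7 and 9.5 at Week 9. Across R of 20% to 80%, exit at Week 5 to 9 and the scenarios where placebo exits exceed avatrombopag exits, the false gap runs from 0.7 points (R 20%, Week 9, 25% vs 10% leaving) to 31.1 points (R 80%, Week 5, 100% vs 0%). Equal exits give zero.

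**Hidden benefit.** Let the placebo hazard be 1.5 times higher, with avatrombopag R = 50%. The full 12-week risks are 50% vs 1 − 0.5^1.5 = 64.6%. With exit at Week 7 and 12% of avatrombopag leaving, crude risks are 48.0% vs 55.1% if half of placebo leaves. They are 48.0% vs 46.1% at the upper bound where every placebo child without durable response leaves (96.6%).

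**Effect of the fix.** Under a constant hazard, expected first events divided by expected time at risk equal h in each arm whatever the exit share. At R = 50% that is 5.8 per 100 subject-weeks in both arms, a rate ratio of 1.00.

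**The case against.** A reader might infer that the plan will produce an artificial excess on avatrombopag, of 4 to 10 points. The documents do not support that. The exit rule covers both arms, Protocol 5.3 words it as optional (Table 3 reads more firmly, and the two passages should be reconciled), and no exit shares are given. The 4 to 10 points hold only if no avatrombopag child leaves, whereas the plan's own response rates imply some non-responders on active drug. The effect is also small if events cluster in the first weeks. This part of the objection stands and sets the wording of the conclusion.

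The comparison is descriptive, with no test. One placebo child is 1/18 = 5.6 points, and at 50% incidence the 95% interval for a difference has a half-width of 1.96 × √(0.25/54 + 0.25/18), about 27 points. Chance may exceed the bias. That limits what anyone can conclude, but the bias is systematic and collected data can address it.

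The plan is not silent on exposure. Duration (SAP 7.5.1) and discontinuations with reasons (SAP 7.2.2) are summarised by arm, and adverse events are listed. A reader will see an imbalance and can approximate a rate per treatment-week from number of subjects times mean duration. Time at risk to a first event cannot be recovered from the planned tables.

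Moving events after open-label dosing out of the placebo count is correct in itself. The Core window is also not a uniform 12 weeks, because children who do not enter the Extension are followed for about 30 more days; the model leaves this out. Finally, rates per subject-week need a roughly constant hazard and do not remove informative exit, since those who leave are the non-responders.

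**Conclusion.** The point holds as a tendency. Crude Core Phase percentages will tend to understate placebo risk if, as the plan's response assumptions suggest, more placebo children leave early. The false gap is about 14.8 points times the difference in exit shares, given equal constant hazards, a 50% 12-week risk and exit at Week 7.5. The documents fix none of these inputs, so the size is open and could be zero. It would go too far to call the planned safety comparison invalid or to predict an excess of a given size. What the documents support is a foreseeable distortion in the only randomised paediatric safety comparison, which the planned adverse event tables show no way to adjust for and which is cheap to address.

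**What to change.** In SAP 7.5.2, beside the crude percentages, add Core Phase exposure-adjusted incidence rates by arm for any TEAE, serious TEAEs and events of special interest. Define the rate as subjects with a first event per 100 subject-weeks at risk, with time at risk ending at the first event, the first open-label dose or the end of Core Phase follow-up, whichever comes first.

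Optionally, add crude incidence to a common early cut-off such as Week 4, before most lack-of-effect exits are possible. This does not depend on a constant hazard and is largely free of informative exit.

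The cost is a few tables from data already collected, with no change to treatment or exit rules. The downside is more output, and rates for rare terms will be unstable with 18 placebo children.
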